We propose a comprehensive management program for postpartum patients with HDP who are at risk for severe maternal morbidity and mortality. Our program will emphasize three key components: 1) self-monitoring of blood pressures with app-based reporting connected to our electronic health record, 2) blood pressure management directed by a program navigator with guideline and physician support and 3) facilitated transitions of care to primary care clinicians for hypertension management. We will randomize 1400 patients with HDP on postpartum day one with follow up through 3 months postpartum. Primary outcome will be blood pressure control at 2 weeks postpartum. Secondary outcomes include identification and treatment of severe blood pressures, severe maternal morbidity, postpartum and primary care visit attendance, and multiple patient-reported outcome measures. All outcomes will be stratified by race (Black and non-Black) to evaluate disparities and by tight versus usual blood pressure control to evaluate the impact of strict postpartum blood pressure control on outcomes. We hypothesize that a comprehensive postpartum HDP management program will improve hypertension control for all patients and reduce disparities that affect Black patients, and that stricter blood pressure control will be associated with fewer adverse outcomes.

OBJECTIVE

Specific Aim 1: To assess whether augmented remote blood pressure monitoring and tight blood pressure control, both individually and in combination, improve blood pressure control and the frequency of severe hypertension in the first 2 weeks postpartum.

Specific Aim 2: To test whether these interventions narrow the existing Black/non-Black inequity in postpartum outcomes such as blood pressure control and severe hypertension.

ELIGIBILITY CRITERIA

Inclusion Criteria

1. Age ≥ 18 years
2. Diagnosed with a Hypertensive Disorder of Pregnancy (HDP), which includes chronic hypertension, preeclampsia, gestational hypertension, HELLP Syndrome (Hemolysis, Elevated Liver enzymes, Low Platelets), or eclampsia (O10, O11, O13, O14, O15, O16)

Exclusion Criteria

1. Not able or willing to receive electronic surveys
2. Deemed inappropriate for study enrollment by bedside nurse
3. Non-English speaking
4. Discharge on postpartum day 6 or greater
5. Contraindication to ACOG-recommended hypertension control (i.e. chronic kidney disease, stroke)

SCREENING

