An Epic Dashboard will be used to screen eligibly patients using the following criteria:

- Admitted to the following units: 4 North, 4 South, 4 East, 4 Med Center East
- Age ≥ 18 years
- Problem list containing the following ICD10 codes: O10, O11, O12, O13, O14, O15, O16
- Preferred language is English

ENROLLMENT

Patients will be approached for enrollment in the study in their private hospital rooms. Research personnel will discuss potentially eligible patients with either the bedside nurse or charge nurse prior to approaching patients to determine any concerns about enrollment.

Recruiting Script: "Hello Ms. [Patient Last Name]. I am [Research Assistant Name] and I am a research assistant at Vanderbilt. I was hoping to talk to you about a study we are doing among patients who have had high blood pressure issues during pregnancy or postpartum."

Patients Who Express Interest: "We want to learn how to better help patients who have high blood pressure in pregnancy. All women who have high blood pressure in pregnancy should see their obstetric provider within one week of leaving the hospital to watch blood pressure closely. We want to learn the best way to provide blood pressure care. If you join the study, you would be placed randomly into a group. You would either see your OB as usual for blood pressure help or manage your blood pressure electronically with help from a special team. You would still see your OB for regular postpartum follow up and questions. You would also be grouped by different blood pressure goals. As part of the study, we will look at your health record to learn about your delivery and any health issues. We only share this information with the research team and not your OB. You will get \$50 if you finish all 3 months of the study. Risks of the study are small but could include over-treatment, meaning that medication to control blood pressure may be given without added benefit to you, and sharing of health information by accident."

Once a patient expresses interest in participating, they will be given the informed consent document electronically delivered (via text web-link or email link to RedCap) and their e-signature will be obtained if they consent to participation.

STUDY PROCEDURES

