- ▶ **Survey 3**: (12-weeks after delivery): Participants will be contacted via SMS text or email to ask about follow up with a primary care physician and chronic hypertension. Participants will receive a \$20 gift card for completion of this survey.

OUTCOMES

Primary Outcomes: The outcome for the R21 and listed on ClinicalTrials.gov is the proportion of patients with a blood pressure recorded in the office at 7-10 days postpartum (**BPinperson**). It is not hypothesized that the primary outcome varies by the blood pressure control intervention but will vary by the blood pressure management intervention.

Secondary Outcomes: We will examine three categories of secondary outcomes (**Table 3**). *Hypertension control and adverse events* includes measures of blood pressure control and events potentially associated with poor blood pressure control such as severe maternal morbidity (SMM) and hospital readmission. Given that our intervention tests different models of care, we will assess *health care utilization* associated with these models including adherence to in-person and remote blood pressure monitoring, medication use, attendance at scheduled visits, and unscheduled visits to an urgent care or emergency room.

We will also examine a variety of *patient-reported outcome measures* especially satisfaction with care. HDP carries not only a risk of long-term health sequelae, but also post-traumatic stress disorder, depression, and anxiety.^{92,93} In a review of patients' experiences with HDP, the potential for worsening or chronic hypertension was associated increased feelings of anxiety and loss of agency.⁹⁴ We hypothesize that augmented remote monitoring and tighter blood pressure control, both individually and in combination, will improve postpartum blood pressure control within the first six weeks postpartum. We also hypothesize that participants, especially Black participants, will find the results of these interventions satisfying and acceptable as they provide a nexus of agency during otherwise stressful life events. Observed reductions in blood pressure provide more frequent and immediate feedback to participants relative to other meaningful outcomes such as SMM or hospital readmission. We also acknowledge the possibility that patients also could find frequent observation of blood pressures and tighter parameters to be burdensome or increase anxiety about health status.

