DBPsevere710_bin	DBP value \geq 110	DBP710 \geq 110	1=yes 0=no
ANYsevere_bin	Any BP value \geq 160/110	SBP710 \geq 160 OR DBP710 \geq 90	1=yes 0=no
dcp_medstart	Any medication started between discharge through week 6 after delivery	n/a	1=yes 0=no
dcpp_medstart	Days postpartum that medication was started	n/a	Continuous
readmit	Hospital readmission	n/a	1=yes 0=no

The two co-primary outcomes are mean systolic blood pressure (SBP) and diastolic blood pressure (DBP) recorded in-office (**Table 3**). In a secondary analysis, we will also include mean blood pressure measurements reported via augmented remote monitoring among women who do not attend in-office visits. The third co-

primary outcome is proportion of participants with sustained severe hypertension during the first 6 weeks postpartum defined as a SBP ≥ 160 or a DBP ≥ 110 on two occasions at least 15 minutes apart.

Secondary Outcomes

We will examine three categories of secondary outcomes (**Table 3**). *Hypertension control and adverse events* includes measures of blood pressure control and events potentially associated with poor blood pressure control such as severe maternal morbidity (SMM) and hospital readmission. Given that our intervention tests different models of care, we will assess *health care utilization* associated with these models including adherence to in-person and remote blood pressure monitoring, medication use, attendance at scheduled visits, and unscheduled visits to an urgent care or emergency room.

Table 3: Study outcomes and time frame for assessment

Hypertension Outcomes		
Blood pressure control (Primary Outcome)	Mean SBP assessed in-office and through all methods	7-10 days
Blood pressure control (Primary Outcome)	Mean DBP assessed in-office and through all methods	7-10 days
Severe hypertension (Primary Outcome)	SBP ≥ 160 or DBP ≥ 110 on two occasions 15 minutes apart and less than 4 hours apart	6 weeks
Hospital readmission	Readmission for hypertension management after delivery discharge	3 weeks
Severe maternal morbidity	Center for Disease Control criteria	6 weeks
Health Care Utilization		
Blood pressure assessment	Proportion who report at least one BP reading post delivery	7-10 days
Medication use	Proportion requiring and/or initiating antihypertensive medications	6 weeks
Urgent care visit	Visit to obstetric triage or an emergency department for hypertension	3 weeks

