The PI will monitor protocol adherence and the progress of the trial on an ongoing basis by reviewing all data collected and monitoring enrollment and follow up. For participants who indicate a high degree of dissatisfaction with the study, the PI will contact the participant to assess the source of the dissatisfaction and whether any postpartum complications have arisen. If complications are uncovered and the participant requires medical care, we will facilitate obtaining care with our providers at Vanderbilt. The PI will notify the Vanderbilt University's Institutional Review Board (IRB) of any AEs promptly and at most within 7 days of the event. If the adverse event is thought to be due to the study, the PI will draft a safety report and send a copy to the IRB who serves as an objective review mechanism. This policy/procedure means that any potential conflict of interest inherent in the PI being the sole reviewer of serious adverse events is avoided. In addition, all research personnel will be asked to contact the PI within 24 hours to report serious adverse events. All SAEs occur during the study defined by the given protocol, regardless of the relation to the research, will be reported to the IRB by telephone, e-mail or fax within 24 hours of the investigator's awareness of the occurrence of the event. All expected non-serious adverse events (i.e. patient dissatisfaction) that occur at a greater frequency or severity than anticipated and all unexpected non-serious adverse events will be reported to the IRB within 15 working days of the investigator becoming aware of the event. Adverse events will be summarized annually in the IRB application for continuation or termination of the research.

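### No outcome is defined for symptomatic low blood pressure or antihypertensive side effects: Table 3 counts readmissions and urgent visits only for hypertension, and no adverse-event comparison by arm is stated

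*Combined protocol and SAP*

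**What the plan says.** All references are to the combined protocol and SAP.

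- **Hypothesis.** The programme overview just before OBJECTIVE closes by expecting that "stricter blood pressure control will be associated with fewer adverse outcomes".
- **Risk told to participants.** The recruiting script under ENROLLMENT says that risks "could include over-treatment, meaning that medication to control blood pressure may be given without added benefit to you".
- **How adverse outcomes are framed.** OUTCOMES describes the hypertension category as blood pressure control plus "events potentially associated with poor blood pressure control such as severe maternal morbidity (SMM) and hospital readmission".
- **Table 3.** Severe hypertension is "SBP ≥ 160 or DBP ≥ 110 on two occasions 15 minutes apart and less than 4 hours apart". Hospital readmission is "Readmission for hypertension management after delivery discharge". Urgent care visit is "Visit to obstetric triage or an emergency department for hypertension". Severe maternal morbidity is by CDC criteria, and medication use is a proportion.
- **Derivation table (7-10 Day Outcomes).** The variable `readmit` is hospital readmission with no reason attached. The OUTCOMES narrative likewise names unscheduled urgent care or emergency room visits without limiting them to hypertension.
- **Direction of benefit (ANALYTIC APPROACH, Aim 1).** A negative coefficient for SBP or DBP is read as better control, and a negative log-odds ratio as an improved outcome. No lower bound is given for blood pressure.
- **Adverse events (DATA AND SAFETY MONITORING).** The definition is broad and needs no judgement of causality. On timing, "The PI will notify the Vanderbilt University's Institutional Review Board (IRB) of any AEs promptly and at most within 7 days" of the event. Later in the same section, unexpected non-serious events have 15 working days, as do "All expected non-serious adverse events (i.e. patient dissatisfaction) that occur at a greater frequency or severity than anticipated". Events are summarised annually for the IRB, with no stated breakdown by arm.

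**The concern.** The two blood pressure goals differ in the level at which medication is started or titrated, so the tight group is by design more exposed to antihypertensives. A hypothesis of fewer adverse outcomes under the tighter goal is tested fairly only if events in both directions are counted. The two Table 3 rows that count acute contacts, readmission and urgent care, admit one direction only.

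The benefit-harm balance of tight control is at stake. A fall in hypertension visits could be offset by visits for low pressure or drug reactions, and the Table 3 analysis would show the fall without the offset. Table 3 and the derivation table also disagree on what a readmission is, so two analysts following the document could report different counts under the same name.

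**Working it through.** **1. The plan's own figures.** Inputs from Power and Sample Size Considerations: 250 v 500, alpha 0.05 (taken as two-sided), 0.22 SD for blood pressure, and 10.2% reduced by 57% for severe hypertension.

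- Blood pressure: SE = √(1/250 + 1/500) = 0.0775 SD. 0.22/0.0775 = 2.84, and Φ(2.84 − 1.96) = 0.81.
- Severe hypertension: 10.2% × 0.43 = 4.39%. The number of controls needed for 80% power is 248 with continuity correction, against 250 stated. Without the correction, power at 250 v 500 is 84%.

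The stated figures reproduce. They concern blood pressure and severe hypertension; neither the text nor Table 6 gives a figure for low blood pressure or a drug side effect.

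**2. Tracing one event.** Take a woman who goes to the ED with symptomatic low blood pressure after starting or increasing medication, without raised pressure.

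| Where it might count | Counted? |
|---|---|
| SBP/DBP at 7-10 days | Not as an event; a lower value is read as better |
| Severe hypertension | No |
| Readmission, Table 3 | No, even if admitted, because hypertension is not the reason |
| `readmit`, derivation table | Yes, if admitted |
| Urgent care visit, Table 3 | No |
| Unscheduled visits, OUTCOMES narrative | Yes, on a literal reading |
| Severe maternal morbidity | Only if it meets the CDC criteria, which the document does not list |
| Medication use | Shows exposure, not the event |
| Adverse event | Recordable, but no comparison by arm is stated |

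The document therefore holds both a wide and a narrow counting rule, and the table that defines the study outcomes uses the narrow one.

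**3. Size under assumed rates.** The documents give no harm rate, so the rates below are assumptions. With p̄ the mean of the two proportions and n per group:

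SE₀ = √(2p̄(1 − p̄)/n); SE₁ = √((p₁(1 − p₁) + p₂(1 − p₂))/n); power = Φ((|p₂ − p₁| − 1.96·SE₀)/SE₁).

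For 2% v 5%, p̄ = 0.035:
- n = 500: SE₀ = 0.01162, SE₁ = 0.01158, z = (0.03 − 0.02278)/0.01158 = 0.62, power 0.73. Expected events: 500 × 0.02 = 10 and 500 × 0.05 = 25.
- n = 250: SE₀ = 0.01644, SE₁ = 0.01638, z = (0.03 − 0.03222)/0.01638 = −0.14, power 0.45.

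| Assumed rates (standard v tight) | 500 v 500 | 250 v 250 |
|---|---|---|
| 2% v 4% | 46% | 26% |
| 3% v 6% | 63% | 37% |
| 2% v 5% | 73% | 45% |
| 2% v 6% | 90% | 63% |

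The 500 v 500 column pools over monitoring arm. The Aim 1 model includes the interaction, so with indicator coding its tight-goal coefficient compares single cells, about 250 v 250. The rate needed in the tight group for 80% power, from 1%, 2%, 5% and 10% in the standard group, is 3.7%, 5.3%, 9.6% and 16.0% at 500 v 500, and 5.4%, 7.3%, 12.0% and 18.8% at 250 v 250.

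**4. What the omission could hide.** At 10 v 25, the tight group has 25 − 10 = 15 extra events. If each led to one visit, they would cancel 15 fewer hypertension visits, and Table 3 as written would report only the 15 fewer.

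**The case against.** A reader might infer that every adverse outcome in the plan counts only under-treatment and that the trial cannot see harm from tight control. The documents do not support that.

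- Severe maternal morbidity is not expressly limited to hypertensive events, `readmit` is unrestricted, and the adverse-event definition would take in hypotension or a drug reaction. Serious events go to the IRB within 24 hours whatever their cause.
- The script defines over-treatment as medication without added benefit, not as fainting or low pressure. Medication use by arm, set against blood pressure and severe hypertension, bears on that directly.
- The plan acknowledges possible burden and anxiety, and Survey 2 collects PROMIS Anxiety, although Table 3 does not list it.

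A reader might also infer that over-treatment, being foreseen, is an expected adverse event reportable only above an anticipated frequency. The section's only example of an expected event is dissatisfaction, so that classification is not established.

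Nor are provider-monitored women without contact. All arms have an in-person check requested at 7-10 days, and these women are told to report symptoms to their clinicians. The remote arms are nevertheless contacted every weekday in weeks 1-2, so spontaneous reports may be ascertained unequally by monitoring arm. Because goal and monitoring are crossed 1:1:1:1, this matters more for the monitoring comparison than for the goal comparison.

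These points limit the concern without removing it: none of these routes is a pre-specified comparison by arm of low-pressure events or side effects. The Appendix J and K algorithm figures are not shown and Appendix L has no readable content, so any handling of low pressure there could not be checked.

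**Conclusion.** The point holds in a limited form. Table 3 restricts readmission and urgent visits to hypertension, no readable outcome covers symptomatic low pressure or antihypertensive side effects, and no adverse-event comparison by arm is stated. Followed as written, the acute-contact comparison between blood pressure goals is one-sided. Table 3 also conflicts with `readmit` and with the narrative on unscheduled visits.

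The conclusion rests on the outcome definitions, not on the power figures. Those depend on assumed rates and show only that a moderately common harm could be compared at the planned size, while a rare one could be compared only if it rose several-fold. It is worth correcting because the change is small and also settles the readmission conflict.

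**What to change.** 1. In Table 3, count all-cause readmission and all-cause triage or ED visits by arm, with the reason coded as hypertension, low blood pressure or medication reaction, or other. Keep the hypertension-only versions as components, and align `readmit`, including its time window, with the Table 3 row.
2. From the same record review in all four arms, report symptomatic low blood pressure or an antihypertensive side effect leading to a visit as a safety outcome by blood pressure goal. Any added Survey 2 items should be supportive only, since participants know their goal and Table 5 assumes 75% retention to 6 weeks.
3. Tabulate adverse events by blood pressure goal and monitoring arm. Reconcile the 7-day and 15-working-day statements so that each type of event has one reporting route.

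**Cost.** Wording in Table 3, the derivation table and DATA AND SAFETY MONITORING, plus one coded field. This assumes that visits and readmissions are taken from the health record, which the recruiting script says will be examined. No treatment rule changes. Because power for rare harms is low, present the comparison descriptively, with event counts and confidence intervals.

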While postpartum patient-reported outcome measures have been developed and validated to study inpatient recovery, lack of consensus exists regarding optimal measures of outpatient recovery.⁹⁵ In a recent systematic review of validated measures used to assess three domains or more of outpatient postpartum recovery, three measures were identified but all had significant limitations.⁹⁶ The authors conclude that assessment may be better achieved using existing methods such as those endorsed by the Patient-Reported Outcomes Measurement Information System initiative (PROMIS).⁹⁶ Therefore, we selected validated PROMIS and NIH Toolbox measures related to depression, anxiety, and social support. Because experience of being listened to or being ignored and dismissed are central drivers of Black women's pregnancy and postpartum experience and health outcomes,^{38,39} we emphasize outcomes related to communication during and satisfaction with clinical encounters such as the Communication Assessment Tool -Team (CAT-T) and the Mothers on Respect index (MORi), a scale developed to assess the nature of respectful patient-provider interactions and their impact on a person's sense of comfort, behavior, and perceptions of racism or discrimination.

VARIABLE NAME	DESCRIPTION	DERIVATION	VALUE
7-10 Day Outcomes			
BPinperson710	BP recorded in person	None	1=yes 0=no
BPMremote710	Any BP recorded remotely	A systolic BP (d710sbp_remote) or a diastolic BP (d710dbp_remote) value is present	1=yes 0=no
BPanyp710	Any BP recorded in person or remotely	If BPinperson710 = 1 or BPMremote710=1	1=yes 0=no
SBP710	SBP value Selected by the following hierarchy: 1) in person SBP, 2) remote SBP - If multiple remote BP values were submitted, selected the SBP from day 8 and average the values.	SBP710 = d710sbp_inperson if d710sbp_inperson is present. If d710sbp_inperson is absent, then use d710sbp_remote.	Continuous
DBP710	DBP value Selected by the following hierarchy: 1) in person DBP, 2) remote DBP - If multiple remote BP	DBP710 = d710dbp_inperson if d710dbp_inperson is present. If	Continuous

	values were submitted, selected the DBP from day 8 and average the values.	d710dbp_inperson is absent, then use d710dbp_remote.	
SBP710_bin	SBP value \geq 140	SBP710 \geq 140	1=yes 0=no
DBP710_bin	DBP value \geq 90	DBP710 \geq 90	1=yes 0=no
ANYhigh_bin	Any BP value \geq 140/90	SBP710 \geq 140 OR DBP710 \geq 90	1=yes 0=no
SBPsevere710_bin	SBP value \geq 160	SBP710 \geq 160	1=yes 0=no

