While postpartum patient-reported outcome measures have been developed and validated to study inpatient recovery, lack of consensus exists regarding optimal measures of outpatient recovery.⁹⁵ In a recent systematic review of validated measures used to assess three domains or more of outpatient postpartum recovery, three measures were identified but all had significant limitations.⁹⁶ The authors conclude that assessment may be better achieved using existing methods such as those endorsed by the Patient-Reported Outcomes Measurement Information System initiative (PROMIS).⁹⁶ Therefore, we selected validated PROMIS and NIH Toolbox measures related to depression, anxiety, and social support. Because experience of being listened to or being ignored and dismissed are central drivers of Black women's pregnancy and postpartum experience and health outcomes,^{38,39} we emphasize outcomes related to communication during and satisfaction with clinical encounters such as the Communication Assessment Tool -Team (CAT-T) and the Mothers on Respect

index (MORI), a scale developed to assess the nature of respectful patient-provider interactions and their impact on a person's sense of comfort, behavior, and perceptions of racism or discrimination.

ENROLLMENT AND FEASIBILITY

During 2021, 22% (n=1120) of patients delivering at VUMC had a diagnosis of HDP, most commonly gestational hypertension, preeclampsia, and chronic hypertension and 22% of these patients were Black. We have used the eligibility, enrollment, and follow up estimates in **Table 5**. With an aim for 50% of our participants to self-identify as Black, we estimate that we can enroll a total sample size of 1000 patients with 6-week follow data after 4-years. Enrollment and follow up estimates are based on prior observational and intervention studies performed among postpartum patients.¹⁰⁰⁻¹⁰²

Table 5 : Estimated Enrollment Numbers

	Black patients annually	Black patients 4 years	Total sample size 4 years
Total deliveries with HDP	246	986	1971
Eligible for study (95%)	234	936	1873
Agree to enroll (75%)	176	702	1404
Retained to 6 weeks (75%)	132	527	1053

ANALYTIC APPROACH

Specific Aim 1: To assess whether augmented remote blood pressure monitoring and tight blood pressure control, both individually and in combination, improve blood pressure control and the frequency of severe hypertension in the first 2 weeks postpartum.

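### Three unreconciled primary-outcome statements: the registered outcome has no power calculation, and the three co-primaries have no any/all rule

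*Combined protocol and SAP*

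**What the plan says.** Three places in the protocol and SAP give a primary outcome.

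- **Study summary, before the Objective section:** a single primary, blood pressure control at 2 weeks postpartum, with no further definition.
- **Outcomes section, first paragraph (headed Primary Outcomes):** the plan names one outcome there, as follows: "The outcome for the R21 and listed on ClinicalTrials.gov is the proportion of patients with a blood pressure recorded in the office". Its variable name is BPinperson and its window is 7-10 days. The plan's next sentence ties it to one factor: "It is not hypothesized that the primary outcome varies by the blood pressure control intervention but will vary by the blood pressure management intervention". The Secondary Outcomes paragraph that follows includes measures of blood pressure control among the secondary outcomes.
- **Text after the variable table:** "The two co-primary outcomes are mean systolic blood pressure (SBP) and diastolic blood pressure (DBP) recorded in-office", with a third co-primary added: "primary outcome is proportion of participants with sustained severe hypertension during the first 6 weeks postpartum". Table 3 marks all three as primary, and the Aim 1 Analytic Approach tests both factors on them.

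The variable table codes BPinperson710 ("BP recorded in person") as 1/0, but Table 3 has no row for it. The nearest row is "Proportion who report at least one BP reading post delivery". That row sits under Health Care Utilization, is not marked primary and is not limited to office readings.

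The only alpha given is the 0.05 in the title of Table 6.

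**The concern.** The three statements differ in outcome, time point and factor. They also differ in who is analysed: an in-office mean exists only for women who attend, while BPinperson710 is defined for everyone randomised. As written, a result on the registered outcome or on any of the three blood pressure outcomes could be presented as the primary finding after the data are seen.

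Within the co-primary set, the plan does not say whether one success is enough or all three are needed. The first reading raises the type I error. The second lowers power below the stated 80%.

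**Working it through.** **Inputs from Power and Sample Size Considerations and Table 6:** 250 v 500; 0.22 SD for SBP and DBP; SBP 138 (SD 17.2) to 134; DBP 83 (SD 11.9) to 80; severe hypertension 10.2% with a 57% reduction (RR 0.43); alpha 0.05. Two-sided testing is my assumption.

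**1. Reproduce the plan's figures.**
- Means: √(1/250 + 1/500) = 0.0775, and 0.22/0.0775 = 2.84. Power = Φ(2.84 − 1.96) = 81%. The detectable effect at 80% is 2.80 × 0.0775 = 0.217 SD, which agrees with 0.22.
- Severe hypertension: 0.102 v 0.43 × 0.102 = 0.0439, difference 0.0581, continuity correction 0.5 × (1/250 + 1/500) = 0.003, pooled SE 0.0189, unpooled SE 0.0212. Power = Φ((0.0581 − 0.003 − 1.96 × 0.0189)/0.0212) = 80% (84% without the correction).

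Both figures spend the full 0.05 on one outcome. Nothing is reserved for the others.

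**2. Any-of-three rule, per factor.** If the outcomes were independent, 1 − 0.95³ = 14.3%. I also simulated three correlated normal test statistics (2,000,000 draws). The correlations are assumptions: SBP-DBP 0.5-0.7, and severe hypertension with each 0.3-0.5. I ran these both as they stand and with the severe-hypertension correlation shrunk by 0.588, because that outcome is a 10.2% binary event. The result is 12.0-13.5%. Counting only false claims of benefit, it is 6.0-6.8% against 2.5%.

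**3. All-three rule, per factor.** There is no inflation. If each outcome has exactly 80% power, joint power is 0.8³ = 51% if independent and 57-63% under the same correlations. The plan's mmHg targets are slightly larger than 0.22 SD: 4/17.2 = 0.233 SD (power 85%) and 3/11.9 = 0.252 SD (power 90%). With severe hypertension at 80%, joint power is 0.85 × 0.90 × 0.80 = 61% if independent and about 65-70% under the correlations.

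**4. Holm within a factor.** The first step is at 0.05/3 (critical value 2.394).
- At 0.22 SD: Φ(2.84 − 2.394) = 67%.
- At RR 0.43: Φ((0.0581 − 0.003 − 2.394 × 0.0189)/0.0212) = 68%.

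**5. Registered outcome.** The plan gives no baseline rate, so I assume 40-70%. Detectable differences at 80% power, two-sided 0.05, continuity-corrected:

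| Contrast | Groups | Percentage points |
|---|---|---|
| Marginal monitoring effect, all 1400 randomised | 700 v 700 | 6.8-7.6 |
| Marginal monitoring effect, the plan's N=1000 | 500 v 500 | 8.0-9.0 |
| Monitoring effect within one goal stratum, 1400 randomised | 350 v 350 | 9.5-10.8 |

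The last row matters because the Aim 1 model contains both factors and their interaction. With 0/1 coding, the monitoring coefficient is the effect within the standard-goal group only, not the marginal effect.

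**The case against.** The strongest defence is that the Outcomes section does contain a complete hierarchy. It names one registered outcome, calls it the primary, gives a factor-specific hypothesis and places blood pressure control among the secondaries. The later text may have been carried over from a larger grant: the power section discusses an Aim 3 that the Objective section does not contain. That is plausible, and it is why the registered outcome is the first option below. But it is inference. Table 3 and the Aim 1 analysis stand as current text, and no sentence says which statement governs.

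A reader might also infer three stronger points that the documents do not support.

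- *The trial runs at a 12-13.5% type I error.* That holds only under an any-of-three rule, which the plan does not state. Co-primary often means that all must succeed, and on that reading there is no inflation.
- *The registered outcome has no analysis method.* It is not named in the Aim 1 text, but the logistic model specified there for binary outcomes covers a 1/0 variable. What is missing is a primary row, a baseline rate and power.
- *Joint power is 57-63% whatever effect is assumed.* That takes exactly 80% for each outcome. At the plan's own mmHg targets it is about 65-70%, which is still short of 80%.

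**Conclusion.** The point holds. Three primary-outcome statements stand together, the registered one is unpowered, and the co-primaries have no decision rule. This follows from the text alone and needs no assumption.

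The size of the consequence is conditional. Per factor, type I error is about 12-13.5% under an any rule (14.3% if independent). Under an all rule, joint power is about 57-63% with each outcome at 80%, or about 65-70% at the 4 and 3 mmHg targets. These figures rest on two-sided testing and on correlations that the documents do not give.

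The plan's separate power figures are arithmetically sound. It should be corrected before any unblinded analysis, because the choice decides what the trial can conclude.

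**What to change.** Before any unblinded analysis, name one governing primary. Make the study summary, Outcomes section, Table 3, Aim 1 analysis, power section and Table 6 agree with it and with the registration.

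**Option 1, closest to the Primary Outcomes paragraph.** Use BPinperson710 in all randomised participants, tested at two-sided 0.05 as the marginal monitoring contrast, averaged over blood pressure goal. State that this is not the 0/1-coded coefficient from the interaction model. Add a Table 3 row, a baseline rate and power. Mean SBP, mean DBP and severe hypertension become key secondary outcomes. The cost is that those three lose confirmatory status and the tight-control factor has no primary test, although Aim 1 covers both factors.

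**Option 2.** Keep the three co-primaries, state any or all, and align the registration. If any, apply Holm within each factor and accept first-step power of about 67% (0.22 SD) and 68% (RR 0.43) at the planned size. If all, replace the separate 80% figures with joint power.

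Either option needs wording and possibly a registry update, with no extra patients.

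Separately, reconcile three definitions that do not bear on the conclusion above:
- Aim 1 speaks of interventions that "improve blood pressure control and the frequency of severe hypertension in the first 2 weeks postpartum", while the co-primary text and Table 3 use 6 weeks for severe hypertension.
- Table 3 requires readings "on two occasions 15 minutes apart and less than 4 hours apart", while the co-primary text has no 4-hour limit.
- The co-primary text makes adding remote readings a secondary analysis, while Table 3's primary rows cover both in-office and all methods.
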